20.2.6 Poolability, Subgroup, and Sensitivity Analysis

To assess poolability by study site, analyses will be done that test whether study site is a predictor of the primary efficacy and safety outcomes. Two regression models will be fit: a linear regression model having RV/LV diameter ratio as the dependent variable, and a logistic regression model having whether major bleeding occurred (as defined by ISTH within 72 hours of initiation of r-tPA infusion) as the dependent variable. Each model will include site as an independent variable and test the hypothesis that study site was a significant predictor of each dependent variable. If the hypothesis tests show that site is not a significant predictor of either outcome, it will be concluded that the study sites do not differ substantially in terms of outcome, and the data from sites will be pooled for analysis of all primary and secondary endpoints.

For the primary endpoints, descriptive statistics by site will be listed: the mean \pm standard deviation, minimum, and maximum RV/LV diameter ratio, and the proportion of patients experiencing major bleeding, will be calculated for each study site and presented in a table to facilitate site comparisons.

If the hypothesis tests reveal site differences for either outcome, analyses will be performed to compare study sites in terms of participant baseline characteristics (e.g., demographics, medical history) as well as other variables that could influence clinical outcome such as eligibility criteria. Analyses of primary and secondary endpoints will be conducted separately for each study site, and the results of the site comparisons will be used to inform how to interpret site-specific results.

Subgroup analyses will be performed to determine if RV/LV diameter ratio and the proportion of patients experiencing major bleeding differ by demographic variables age,

race, and gender. Summary statistics (mean \pm standard deviation, minimum, and maximum RV/LV diameter ratio, and the proportion of patients experiencing major bleeding) will be calculated for each demographic subgroup and presented in a table to facilitate group comparisons. Regression models will be fit (linear regression for RV/LV diameter ratio, logistic regression for major bleeding) having each primary endpoint as the dependent variable and demographic group as the independent variable. A separate regression model will be fit for each combination of endpoint and demographic variable to formally test the hypothesis of subgroup differences in each primary endpoint.

Sensitivity analyses will be undertaken to assess the impact of missing data for the primary endpoints. The methods for this analysis are described in detail in Section 8 of the Statistical Analysis Plan (THRO-STAT-2019-01), “Handling of Dropouts and Missing Data.” If subjects become COVID-19 positive after enrollment and during the study, a subgroup analysis will be performed. Refer to Statistical Analysis Plan (SAP) (THRO-STAT-2019-01) for additional details.

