6.4 Study Duration

6.4.1 Enrollment

It is estimated that up to 20 sites will be qualified to participate; they will enroll and treat up to 125 subjects (to achieve 100 evaluable subjects) over an estimate of 24 months. There may be an unlimited number of subjects consented for this study to achieve completion of 100 evaluable subjects. A maximum of 125 subjects will be enrolled, treated, and complete the study through 30-day follow-up. The subjects enrolled and treated per site will not exceed 20 subjects.

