20.2 Endpoints, Hypotheses, and Analytical Methods

20.2.1 Primary Efficacy Endpoint:

The primary efficacy endpoint is reduction in the chest CT-measured RV/LV diameter ratio assessed by contrast enhanced chest CT from baseline within 48 ± 6 hours of initiation of treatment.

20.2.2 Hypothesis:

The predicate device for Bashir Endovascular Catheter is the EkoSonic Endovascular System (EKOS, Bothell, WA). The SEATTLE II Study reported a reduction in RV/LV diameter ratio of -0.42 ± 0.36 (mean ± SD) in 115 patients who underwent a within-window CT measurement of RV/LV diameter ratio. We hypothesize that RV/LV diameter ratio measured at 48 hours compared with measured ratio at baseline will be reduced on average by more than 20%.

20.2.2.1 Analytical methods: A change score d will be calculated:

$$d = \frac{R_{48} - R_0}{R_0}$$

that expresses the change as a proportion of the baseline value, where R_0 and R_{48} are $\frac{RV}{LV}$ at time 0 and 48 hours post-treatment, respectively. A larger decrease from baseline will result in a change score with a greater magnitude and a negative sign. The change score will be compared to the benchmark value of 20% in a one-sided hypothesis test:

$$H_0: d \geq -0.2$$

$$H_A: d < -0.2$$

The distribution of the change score will be examined to assess whether the normality assumption is met, using both graphical methods (Q-Q plots and histograms) as well as multiple hypothesis tests of normality (Shapiro-Wilk, Kolmogorov-Smirnov, Anderson-Darling, and Cramer-von Mises). Multiple hypothesis testing methods will be employed to assess normality because the choice of the most powerful test depends on the distributional qualities of the data; if the different tests do not result in the same conclusion, more weight will be given to the method that is best suited to the observed distributional qualities of the data (e.g., heaviness of tails). If the data are determined to be normal based on these methods, a t test will be done; if not, a one-sample Wilcoxon

signed rank test (the non-parametric alternative to the one-sample t test) will be done. In addition, the t-test will be presented for the primary endpoint analysis regardless of the normality of the test results.

The test will be performed twice: once at the interim analysis (with $\alpha=0.0038$) and once at the final analysis (with $\alpha=0.0212$). If the p-value is less than α at either analysis, then the test will be considered statistically significant.

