20.2.3 Primary Safety Endpoint:

The primary safety endpoint is major bleeding within 72 hours of procedure initiation of r-tPA infusion (the start of the infusion). Bleeding events are classified by the International Society of Thrombosis and Hemostasis (ISTH).

20.2.4 Hypothesis:

The comparator device for Bashir Endovascular Catheter is the EkoSonic Endovascular System (EKOS, Bothell, WA), and results from the study evaluating the safety and efficacy of this device were the basis for the performance goal of 14.9% proposed for this study. The SEATTLE II Study reported a 10% (standard error=2.45%) of moderate to severe bleeding in treated subjects within 72 hours of the treatment initiation. The hypothesis is that the bleeding rate in this study will not exceed $10\% + 2*SE = 14.9\%$. A one-sided, one-sample exact test of a binomial proportion p will be used to test the hypotheses below.

$$H_0: p \geq 0.149$$

$$H_A: p < 0.149$$

The hypothesis test for the primary safety endpoint will not be done at the interim analysis, but only at the end of the study. This test will have a type I error rate of 0.025.

20.2.5 Secondary Endpoints:

Descriptive statistics will be generated for the secondary endpoints listed below. For continuous measures (e.g., Modified Miller Index comparing 48 hours post therapy to baseline), the mean and 95% confidence limits will be calculated, along with the median, standard deviation and range. For frequency outcomes (e.g., device success), results will be reported as the overall frequency of occurrence as well as the percentage of subjects.

1. Device Success: The number of devices with therapy delivered without a device failure.
2. Refined Miller Score as measured on contrast enhanced chest CT (CTA) within 48 hours after the completion of the r-tPA infusion compared to baseline as measured by core lab.
3. All-cause mortality at hospital discharge through 30-day follow-up.

4. SAEs through 30-day follow-up.
5. AEs through 30-day follow-up.
6. UADEs through 30-day follow-up.
7. Recurrent PE through 30-day follow-up.
8. Clinically Relevant Non-Major bleeding: Any sign or symptom of hemorrhage (e.g. more bleeding than would be expected for a clinical circumstance, including bleeding found by imaging alone) that does not fit the criteria for the ISTH definition of major bleeding but does meet at least one of the following criteria:
 - a. Requiring medical intervention by a healthcare professional.

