20.3 Analysis Populations

All enrolled subjects who receive the study treatment will be included in the Intent-to-Treat (ITT) population. The ITT will consist of subjects who both provide informed consent to participate and have the BEC (or first of two BECs for bilateral PE) introduced into the sheath. The modified ITT (mITT) population are evaluable subjects defined as members of the ITT who have data available to assess the primary efficacy endpoint of reduction in RV/LV ratio as measured by contrast-enhanced chest CT (CTA) at screening and RV/LV ratio as measured by contrast-enhanced CTA at 48 hours after completion of r-tPA treatment. The patients comprising the mITT population are evaluable patients. Members of the ITT population who remain in the study long enough to complete the 30-day follow-up period will comprise the Per-Protocol (PP) population.

The mITT population will be used to analyze the primary efficacy endpoint. The ITT population will be used to analyze the primary safety endpoint, as well as all secondary safety and device endpoints that do not require 30 days of follow-up (e.g., device success, clinically relevant non-major bleeding, technical procedural complications). The PP population will be used to analyze secondary endpoints that require 30 days of follow-up: all-cause mortality, SAEs, AEs, UADEs, and recurrent PE through 30-day follow-up).

Up to 125 subjects, in up to 20 sites, will be enrolled and treated, with the objective to have at least 100 subjects complete the 30-day follow-up period, and be included in the primary efficacy analysis. Each site will have an enrollment cap such that no more than 20% (n=20) of participants are enrolled at a single site.

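### Section 20.2.6 lets a significant site test replace the pooled primary analyses with per-site analyses that cannot settle either primary hypothesis

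*Combined protocol and SAP*

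**What the plan says.** Section 20.2.6 fits two models with site as predictor: a linear regression for the RV/LV diameter ratio and a logistic regression for ISTH major bleeding within 72 hours. If site is not significant for either outcome, "the data from sites will be pooled for analysis of all primary and secondary endpoints". The other branch begins "If the hypothesis tests reveal site differences for either outcome". It asks for a comparison of baseline characteristics across sites and then states: "Analyses of primary and secondary endpoints will be conducted separately for each study site". The site comparisons are to guide the reading of the site-specific results. No significance level or type of test is given for the site tests.

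The sections that define the primary analyses carry no site condition:

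- 20.2.2 (efficacy): "The test will be performed twice: once at the interim analysis" at 0.0038, and again at the final analysis at 0.0212.
- 20.2.4 (safety): a one-sided "one-sample exact test of a binomial proportion p will be used to test the hypotheses below", against 14.9% at 0.025.
- 20.3: "The mITT population will be used to analyze the primary efficacy endpoint"; "The ITT population will be used to analyze the primary safety endpoint".
- 20.1 sizes the trial as one sample, with 83 subjects for 80% power.

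Section 6.4.1 limits site size: "The subjects enrolled and treated per site will not exceed 20 subjects". Up to 20 sites may take part.

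**The concern.** One significant site test, on either outcome, moves both primary endpoints and all secondary endpoints to separate site analyses. In that branch nothing turns a set of site results into an answer for the trial. The defining sections still describe one test per endpoint on everyone, so the reader cannot tell whether the pooled test remains primary.

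Both ways out are bad. If the fallback is followed, the study-level hypotheses go unanswered, because the sites are too small. If it is not followed, the decision to rely on pooled rather than per-site results is taken with the outcomes in view, which weakens the stated type I error rates. With no combining rule, a single favourable site among many could also be put forward although it arose by chance.

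**Working it through.** **Inputs.** From 20.1: assumed reduction 28%, goal 20% (difference 8 points), SD 25 points, one-sided alpha 0.0212 at the final analysis, attrition 20%, 125 treated for 100 evaluable. From 20.2.4: goal 14.9%, one-sided alpha 0.025, exact binomial test. From 6.4.1 and 20.3: at most 20 subjects per site, up to 20 sites.

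**1. Reproduce the plan's sample size.** For a one-sided one-sample t-test, power = 1 − F(t*), where t* is the 1 − 0.0212 quantile of t with n − 1 degrees of freedom and F is the noncentral t distribution with noncentrality (8/25)√n = 0.32√n. The smallest n with at least 80% power is 83 (power 80.2%), as 20.1 states. At 100 evaluable subjects the power is 87.2%.

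**2. Efficacy at one site, same formula.**

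| Evaluable at the site | Basis | Power |
|---|---|---|
| 5 | 100 / 20 sites | 7.0% |
| 16 | cap of 20 less 20% attrition | 20.2% |
| 20 | cap, no attrition | 25.0% |
| 100 | pooled | 87.2% |

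A site with one evaluable subject cannot be tested at all.

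**3. Safety at one site.** The smallest possible p-value comes from zero bleeds: p = (1 − 0.149)^n = 0.851^n.

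- n = 5: 0.446
- n = 20: 0.0397, above 0.025
- n = 22: 0.0287
- n = 23: 0.0245, the first value below 0.025

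At least 23 bleed-free subjects are needed and the cap is 20, so no site can reject, whatever its data. Pooled over 125 subjects, up to 10 bleeds meets the goal: P(X ≤ 10 | n = 125, p = 0.149) = 0.0153.

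**4. A chance success at one or more sites.** Suppose the true reduction is exactly 20% and each site is tested at 0.0212.

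- 20 sites: 1 − (1 − 0.0212)^20 = 34.9%
- 7 sites, the fewest that can hold 125 at 20 each (125/20 = 6.25): 1 − (1 − 0.0212)^7 = 13.9%

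**5. How often chance alone triggers the fallback.** This rests on assumptions, since the plan gives neither the level of the site tests nor a true bleeding rate. With two independent tests at exactly 0.05, the rate is 1 − 0.95² = 9.75%. The bleeding test does not hold its nominal level when events are sparse, so the rate was also simulated: 40,000 trials per setting, no site effect, 125 treated and 100 evaluable in near-equal sites, independent outcomes, an F test for efficacy and a likelihood-ratio test for bleeding, each at 0.05.

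| Assumed bleeding rate | 20 sites | 10 sites |
|---|---|---|
| 5% | 5.1% | 7.2% |
| 10% | 8.3% | 11.9% |
| 12% | 10.6% | 13.1% |

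Real site differences would trigger the same branch in addition.

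**The case against.** The best defence is that the study-level tests are plainly meant to be primary. Section 20.2.2 gives a success criterion without a site condition, and 20.2.4 speaks of the bleeding rate in the study. Section 20.3 aims for at least 100 subjects in the primary efficacy analysis, which no site could supply. Section 20.2.6 never withdraws those tests and ends on interpretation, so its per-site analyses could be read as additional. That may well be the intention, but the wording does not support it: pooling is made the consequence of non-significant site tests, and the separate analyses expressly cover the primary endpoints.

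Several narrower points stand as limits:

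- The harm arises only if the per-site analyses replace the pooled ones.
- The impossibility is exact for safety. For efficacy a site can reject, but with low power.
- No text says that one significant site would count as trial success. The 34.9% and 13.9% show what the missing rule leaves open, and assume that every site can be tested.
- The upper end of the trigger range belongs to the likelihood-ratio test. An approximate Wald test rejects for bleeding in 0 to 0.1% of trials, leaving a trigger rate of about 5%.
- The trigger and its consequence are written in advance, so following them is data-dependent but not a free choice. The post hoc element enters if the rule is set aside.
- The separate plan THRO-STAT-2019-01 was not available for this check and may hold a rule. Section 20.2.6 cites it for missing data and COVID-19, not for pooling.

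**Conclusion.** The concern holds. As written, 20.2.6 makes the pooled primary analyses conditional on site tests of unstated level, contrary to the unconditional tests and populations in 20.2.2, 20.2.4 and 20.3. Its fallback cannot decide the trial: the safety goal is out of reach at every site, and site-level efficacy power is at most 25% against 87% pooled. These results use only the plan's own assumptions and caps. The 5% to 13% chance of a spurious trigger depends on the assumed level, test and bleeding rates, but the conclusion does not depend on it. The protocol wording is certain; what the separate SAP says is not known. This should be fixed.

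**What to change.** State in 20.2.6 that the pooled analysis over all sites, mITT for efficacy and ITT for safety, is the primary analysis of both primary endpoints whatever the site tests show. Delete the switch to separate per-site primary analyses.

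Keep the site tests and by-site tables as descriptive assessments of heterogeneity, with the level stated. For efficacy, run the site test on the change score d, which is what the primary test uses; 20.2.6 now names the RV/LV ratio itself. For bleeding, name a likelihood-ratio or exact test, because the Wald test has almost no ability to reject with so few events. If heterogeneity appears, add a site-adjusted pooled estimate as a sensitivity analysis. Put the same wording in THRO-STAT-2019-01.

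The cost is a sentence or two in each document and a little programming. No extra patients or data are needed.

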20.3 Analysis Populations

All enrolled subjects who receive the study treatment will be included in the Intent-to-Treat (ITT) population. The ITT will consist of subjects who both provide informed consent to participate and have the BEC (or first of two BECs for bilateral PE) introduced into the sheath. The modified ITT (mITT) population are evaluable subjects defined as members of the ITT who have data available to assess the primary efficacy endpoint of reduction in RV/LV ratio as measured by contrast-enhanced chest CT (CTA) at screening and RV/LV ratio as measured by contrast-enhanced CTA at 48 hours after completion of r-tPA treatment. The patients comprising the mITT population are evaluable patients. Members of the ITT population who remain in the study long enough to complete the 30-day follow-up period will comprise the Per-Protocol (PP) population.

The mITT population will be used to analyze the primary efficacy endpoint. The ITT population will be used to analyze the primary safety endpoint, as well as all secondary safety and device endpoints that do not require 30 days of follow-up (e.g., device success, clinically relevant non-major bleeding, technical procedural complications). The PP population will be used to analyze secondary endpoints that require 30 days of follow-up: all-cause mortality, SAEs, AEs, UADEs, and recurrent PE through 30-day follow-up).

Up to 125 subjects, in up to 20 sites, will be enrolled and treated, with the objective to have at least 100 subjects complete the 30-day follow-up period, and be included in the primary efficacy analysis. Each site will have an enrollment cap such that no more than 20% (n=20) of participants are enrolled at a single site.

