3.0 TERMS AND DEFINITIONS (CONTINUED)

TERM	DEFINITION
HIT	Heparin induced thrombocytopenia
Hr	Hour
Hrs	Hours
IJ	Internal jugular
INR	International normalized ratio
LCFV	Left common femoral vein
LMWH	Low molecular weight heparin
NOAC	Non-vitamin K oral anticoagulants; such as rivaroxaban (Xarelto®), apixaban (Eliquis®), dabigatran (Pradaxa®), edoxaban (Savaysa®).
PAD	Pulmonary artery diastolic pressure
PaO₂	Partial pressure of arterial oxygen
PAP	Pulmonary artery pressure
PAS (PASP)	Pulmonary artery systolic pressure
PE	Pulmonary embolism
PMCDT	Pharmaco-mechanical catheter directed thrombolysis
Procedure Start Time	Procedure start time refers to the PMCDT (BEC) procedure and is defined as the injection of local anesthetic at the access site prior to sheath placement in the IR suite / cath lab.
RCFV	Right common femoral vein
Recurrent PE	Recurrent PE is defined as symptomatic and objectively confirmed with contrast-enhanced chest CT or invasive contrast pulmonary angiography.
Refined Modified Miller Score (RMMS)	Like the Modified Miller (MM) score, the Refined Modified Miller score (RMMS) regards each lung as having 10 segmental arteries, and the degree of obstruction of the segmental pulmonary arteries is measured using an ordinal scale. In contrast to the MM, however, the RM score allows for a finer distinction of partial obstruction in seven major arteries; the main pulmonary artery, left and right pulmonary artery, left and right interlobar arteries, left and right basal trunks. Partial obstruction is classified into three categories based upon cross-sectional diameter reduction: 0.5 for 1–33%, 1.0 for 34–66%, and 1.5 for 67–99% obstruction. As in the MM scoring system, the weighted score of the major supplying artery is compared with the sum of its tributaries, and the larger number is recorded. For example, if thrombus obstructed the lumen of a basal trunk vessel by 50% (score = 1.0 x 7), but its four segmental tributaries were fully occluded (score = 2.0 x 4), the higher value of 8 would be recorded as the RMM score. A cumulative score is calculated by summing the scores for all arteries. Similar to the MM score, the RMM score can range from 0 to 20 per lung, for a maximum of 40 bilaterally. ²⁵

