9.3 Summary of Procedure Steps

1. Using a .035in exchange length wire, insert the wire into a sheath and advance it up to the right atrium.
2. Insert the Swan-Ganz or angled pigtail catheter over the wire and advance it up to the right atrium.
3. Remove the guidewire.
4. Float the Swan-Ganz catheter or angled pigtail into the pulmonary artery and record baseline hemodynamic data

5. Insert the exchange length guidewire, or equivalent, into the Swan-Ganz or angled pigtail catheter. Remove the Swan-Ganz or angled pigtail catheter.
6. Exchange the Swan-Ganz Catheter, or angled pigtail, for a long 7F or greater sheath (CFV access) or 7F sheath (IJ access) which is placed into the PA where the thrombus is located.
7. Remove the guidewire and the dilator carefully from the PA making sure that the sheath does not jump forward.

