9.3.1 Intra-procedure Data Collection Requirements

1. Hemodynamic readings
2. AEs / SAEs
3. Times of pulse sprays administration
4. Time the r-tPA infusion(s) started
5. Time of heparin infusion(s) started
6. Technical complications
7. Medications (antiplatelet, anticoagulant, cardiac medications, and NSAIDs only)
8. Equipment used
9. Blood pressure and heart rate, at start of procedure

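### A procedure stopped before the BEC enters the sheath is in no section 20.3 analysis set, so a complication that stops it there enters no secondary safety rate

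*Combined protocol and SAP*

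**What the plan says.** Section 20.3 defines three analysis sets.

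- **ITT.** The opening sentence reads "All enrolled subjects who receive the study treatment will be included in the Intent-to-Treat (ITT) population". The next sentence makes this operational: "subjects who both provide informed consent to participate and have the BEC (or first of two BECs for bilateral PE) introduced into the sheath".
- **mITT.** "The modified ITT (mITT) population are evaluable subjects defined as members of the ITT", with the further condition that both RV/LV measurements are available.
- **PP.** "Members of the ITT population who remain in the study long enough to complete the 30-day follow-up period will comprise the Per-Protocol (PP) population".

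The same section assigns endpoints to sets. ITT is used for the primary safety endpoint and for "all secondary safety and device endpoints that do not require 30 days of follow-up (e.g., device success, clinically relevant non-major bleeding, technical procedural complications". PP is used for all-cause mortality, SAEs, AEs, UADEs and recurrent PE through 30 days. No safety set based on the start of the procedure is defined.

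Section 3.0 places the start of the procedure at the "injection of local anesthetic at the access site prior to sheath placement in the IR suite / cath lab". Data collection during the procedure (section 9.3.1) includes AEs/SAEs and "Technical complications". Section 20.2.5 reports frequency outcomes as counts and as a percentage of subjects.

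**The concern.** Several invasive steps lie between the start of the procedure and entry into ITT. The protocol treats harm from the procedure as study harm. It lists anticipated procedure-related events separately (Table 5), grades procedure-relatedness separately (Table 7), and makes technical procedural complications a secondary endpoint. Yet the rates for these outcomes are conditional on reaching BEC entry.

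This makes inclusion depend on the outcome. Suppose two subjects have the same complication during catheterisation of the pulmonary artery. In one the operator continues and the BEC goes in, so the event is counted. In the other the complication ends the procedure, and neither the subject nor the event appears in any rate assigned by section 20.3.

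Section 6.4.1 sets no limit on the number consented to reach 100 evaluable subjects, so a subject lost in this way is simply followed by another. Section 20.3 does not ask for such cases to be tabulated. A reader who wants to know how often the whole catheter-directed procedure causes complications could therefore be given a rate that is too low.

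**Working it through.** **Order of steps against entry into ITT**

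1. Local anaesthetic: procedure start (section 3.0).
2. Venous access with ultrasound guidance, then sheath placement (section 9.1).
3. "Float the Swan-Ganz catheter or angled pigtail into the pulmonary artery and record baseline hemodynamic data" (section 9.3, step 4).
4. Exchange for a long sheath placed in the pulmonary artery (section 9.3, step 6).
5. BEC preparation, and loading on the wire with an instruction not yet to insert it (section 9.4, steps 2 to 4).
6. r-tPA infusion started through the BEC while it is still outside the sheath (section 9.4, step 6).
7. BEC enters the sheath: ITT entry (section 20.3).

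**Set logic.** A subject stopped during steps 1 to 6 fails the ITT condition. Because mITT and PP contain only ITT members, that subject is in none of the three sets. The contribution to the technical-complication rate (ITT) and to the AE, SAE and mortality rates (PP) is zero in both numerator and denominator.

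**Primary safety endpoint.** Its 72-hour window opens at the start of the r-tPA infusion (step 6), just before ITT entry. Complications of steps 1 to 5 that end the procedure precede that window, so the primary test is essentially untouched.

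**Size.** The plan states no abort rate or complication rate, so it has no figure of its own to reproduce here. The denominator used is the planned maximum of treated subjects, which follows from section 20.1: 100 / (1 - 0.20) = 125.

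Let N be ITT subjects, x their counted complications, a the aborts before BEC entry caused by a complication, and b the aborts for other reasons. Then:

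- ITT rate = x / N
- rate over all started procedures = (x + a) / (N + a + b)

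The values of x, a and b below are assumptions.

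| x (ITT rate) | a | b | All started | Ratio to ITT rate |
|---|---|---|---|---|
| 2 (1.6%) | 0 | 0 | 2/125 = 1.6% | 1.00 |
| 2 (1.6%) | 1 | 0 | 3/126 = 2.4% | 1.5 |
| 2 (1.6%) | 3 | 0 | 5/128 = 3.9% | 2.4 |
| 2 (1.6%) | 0 | 3 | 2/128 = 1.56% | 0.98 |
| 10 (8.0%) | 1 | 0 | 11/126 = 8.7% | 1.09 |
| 10 (8.0%) | 3 | 0 | 13/128 = 10.2% | 1.27 |

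**Direction.** (x + a)/(N + a + b) exceeds x/N when N·a > x·(a + b), that is, when a/(a + b) > x/N. The ITT rate is too low when the share of aborts caused by a complication exceeds the complication rate in ITT, and slightly too high otherwise.

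**AE, SAE and mortality rates.** These use PP, whose size and event counts are not given, and PP also drops ITT members who do not complete 30 days. The table does not carry over to them, and no range is offered.

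**The case against.** The strongest reply is that no safety information is lost. Participation runs from consent through 30-day follow-up (section 6.4.6), all AEs go on the case report form (section 17.3), and SAEs of any cause must be reported (section 17.5). The DSMB reviews all reported AEs (section 21.0). The intracranial haemorrhage rule refers to patients undergoing the investigational procedure rather than to ITT (section 22.2.1), and device failures that prevent treatment count toward a pause (section 22.3.2). The affected endpoints are descriptive, and a device-entry denominator is defensible when the objective is the safety of the catheter. All of this stands, and it limits the point to tabulation. It does not answer it, because none of these provisions supplies a denominator for an endpoint reported as a percentage of subjects.

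A reader might also infer more than the documents support:

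- **That the reported rates can only be too low.** This holds for aborts caused by a complication. Aborts for other reasons, such as a BEC that fails its preparation check, add only to the denominator.
- **That the omitted cases are the worst, or that Table 5 mostly describes the steps before BEC entry.** Table 5 gives no timing. It includes events such as heparin-induced thrombocytopenia and warfarin skin necrosis that are not specific to access or catheterisation.
- **That the true rate is about 1.5 to 2.4 times the reported one.** That multiplier comes from assuming 2 counted events. With 10 it is about 1.1 to 1.3.
- **That BEC entry is the main cause of loss in the AE, SAE and mortality rates.** PP completion is a second restriction on the same rates, and it can remove treated subjects, including those who die. The documents do not show which matters more.

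The separate SAP might define a further safety set. That cannot be excluded, but such a set would have to be reconciled with the explicit assignments in section 20.3.

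**Conclusion.** The point holds for protocol section 20.3. A complication that stops the procedure between local anaesthetic and BEC entry is collected and reviewed but enters no rate assigned there, whereas the same complication is counted if the procedure goes on. This is outcome-dependent selection written into the set definitions. It affects secondary descriptive rates only; the primary efficacy and safety tests and the sample size do not change.

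The net size depends on the number and mix of aborts, which are unknown. In the technical-complication illustration, the change runs from a trivial fall (1.6% to 1.56%) to a rise of about 2.3 percentage points (1.6% to 3.9%; 8.0% to 10.2% is about 2.2 points). It assumes 125 ITT subjects, 2 or 10 counted events and at most 3 aborts. With no aborts the gap has no effect. The correction is cheap and should be made before analysis.

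**What to change.** In section 20.3, with matching text in the SAP:

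- Add a procedure-attempted safety set: all consented subjects from procedure start as section 3.0 defines it, whether or not a BEC was introduced.
- Report technical procedural complications, procedure-related AEs/SAEs and mortality in this set, without requiring completion of 30 days.
- State the number of procedures stopped before BEC entry, with reasons, so that aborts caused by a complication can be told apart from the others.
- State that these subjects are included in the existing 30-day AE contact.
- Keep ITT for the primary safety test and for device success.

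The cost is one more denominator, a few follow-up contacts and possibly slightly less favourable rates. The data collected during the procedure already cover what is needed.
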